3.3.4.2. Efficacy study

Since this is an observational study, all analyses must take confounding into account. For each outcome, a Direct Acyclic Graph (DAG) will be prepared, discussed by surgeons and epidemiologists, i.e. a graph that allows hypothesizing the causal relationship between intervention and outcome taking into account potential confounding factors, measurable or not. On the basis of this graph, which underlies a causal model, the variables to be included in the multinomial regression model will be selected for estimating the probability of being treated with each surgical modality as a function of potential confounders (known as propensity score). Among the variables that will be considered to define the DAGs are age, gender, performance status, treatment center and tumor characteristics. The inverse of this estimated probability will be used as weight in the regression models (inverse probability weighted, IPW) which will have the outcome as the dependent variable and the treatment modality as the independent variable: robotics, VATS and thoracotomy (reference). Differences in the duration of surgery and hospitalization will be analysed using an IPW generalized linear regression model. The 30-day odds ratio (OR) of death for VATS and robotic surgery versus thoracotomy will be estimated by means of an IPW logistic regression model. Relative survival will be evaluated using a Cox IPW model and expressed both in terms of hazard ratio (HR) and as one and 5 year survival. For inpatient reoperation, the need for conversion to thoracotomy for VATS vs. robotic surgery and major complications by type of surgery, which are expected to be rare events, a we will consider a IPW zero-inflated (Poisson or negative binomial) approach. All estimates will be presented together with 95% confidence intervals obtained from a robust standard error [39]. The same analyses, if allowed by the study number, will be repeated in the three surgical subgroups (atypical and segmental resection, lobectomy, pneumonectomy), in subjects aged less than or equal to 65 years vs. superior, in patients with performance status of 0 vs. 1 vs. 2. Sensitivity analyses will be carried out using alternative models for the probability of estimating the type of intervention.

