3.3.2.2. Safety

- 30-day mortality
- Reoperation during hospitalization
- Need for conversion to thoracotomy for VATS and robotic surgery
- Major complications by type of surgery (Table 3)

Secondly, differences in terms of duration of operation and hospitalization will be evaluated. This information will be used for the cost-effectiveness assessment.

 Table 3 Complications of interest and related ICD-9-CM codes

COMPLICATION	CODE
Iatrogenic cerebrovascular infarction or hemorrhage	997.02
Central nervous system complication (Brain anoxic damage, Cerebral hypoxia)	997.01
Cardiac complications, not elsewhere classified	997.1
(Cardiac: arrest, insufficiency, cardiorespiratory insufficiency, heart failure)	
Post traumatic pulmonary insufficiency	518.5
Urinary complications, not elsewhere classified (Renal: Acute defaillance, acute failure, acute tubular necrosis specified as due to interventions)	997.5
Postoperative infection, not elsewhere classified	998.5x
Hemorrhage or hematoma or seroma complicating a procedure, not elsewhere classified	998.1x
Persistent postoperative fistula	998.6

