3.3.3. Collected variables

3.3.3.1. From administrative databases

The staff of the Epidemiology Unit involved in the study will extract the information specified in Table 4 from the current administrative databases of the ATS of Milan. Subsequently, it will perform the deterministic record linkage on a unique key (fiscal code) and will anonymize the dataset for the analysis, removing the tax code, deleting the dates once the time intervals necessary for the analysis have been calculated (age, length of hospitalization, length of post-operative stay, etc.), and assigning a random ID to the patient. Separate copy of correspondence between social security number and random id will be kept in a separate password protected file.

Data flow	Data relating to	Variables
Hospital Discharge	Patient	Civil status, study level
Summary (SDO)	Hospital admission	Admission date, intervention date, discharge date, type of discharge, within hospital transfers
	Diagnoses and complications	All ICD-9-CM diagnosis codes present in a SDO
	Procedures	DRGs, ICD-9-CM procedure codes, procedure date
Patient registry	Patient	Sex, birth date, city of residence, vital status at 2022/12/31
SDO, outpatient services, pharmaceuticals, exemptions	Patient comorbidities	Charlson comorbidity index calculated through the algorithm in use at the Epidemiology Unit
Cancer registry	Cancer	Histology (morphological code ICDO3, margins of resection, number of mediastinal lymph nodes removed, number of positive mediastinal lymph nodes, stage at diagnosis)

Table 4 Variables collected from administrative databases

3.3.3.2. From the data provided by the centers through a dedicated platform made available by the ATS of Milan

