The Epidemiology Unit of the ATS of Milan has an IT platform, which can display the list of their patients included in the study only to clinicians who have or have had the patient in treatment. The same platform allows the clinicians in charge to view the information relating to the patient and pertinent to the study in question. Information can be derived from the administrative databases and from the internal databases of the center. The platform will also allow to fill in an ad hoc questionnaire, which will be piloted on 2 patients per center, for the collection of additional data necessary for the study. The information collected will form a database that will be linked via fiscal code to that derived from administrative flows passing through the third table of correspondence between random id and fiscal code. The questionnaire will collect the following information (details in the data collection form, Annex 2). Part of the information necessary for the study will be acquired by the Epidemiology Unit of the ATS of Milan directly from available internal information flows of the participating Centers. Specifically, this is information collected by the participating Centers in the context of collaboration with important projects for the construction of European and Italian registries (such as those of the ESTS (European Society of Thoracic Surgeons) and the Study Group and Italian Register of VATS Lobectomy) or which can be extracted by participating centers from computerized medical records. The participating centers will select the subjects included in this study and the variables included in the CRF of the same.

Data relating to:	Variables
Intervention	Surgical approach - Open - VATS
	 Need for conversion to thoracotomy

Table 5 Variables collected at participating thoracic surgery centers

Patient	 Equipment used (brand and model) Computer-assisted Need for conversion to thoracotomy Equipment used (brand and model) Smoking habit Performance status
Complications	See Table 3

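### Rarity does not justify zero-inflated count models: conversion is yes/no per operation, and the IPW logistic model already planned for 30-day death suits it better

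*Combined protocol and SAP*

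**What the plan says.** Section 3.3.2.2 (Safety) lists four outcomes. One is 30-day mortality. The other three are "Reoperation during hospitalization", "Need for conversion to thoracotomy for VATS and robotic surgery" and major complications, the last defined by the ICD-9-CM codes in Table 3.

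Section 3.3.4.2 gives 30-day death an IPW logistic model with an odds ratio. It groups the other three, "which are expected to be rare events, a we will consider a IPW zero-inflated (Poisson or negative binomial) approach". No further reason is given: the section does not mention structural zeros, overdispersion or repeat events. It names no alternative model and no effect measure for these outcomes. The weighted regression models are described earlier in the section as ones "which will have the outcome as the dependent variable and the treatment modality as the independent variable". Confounders therefore enter through the weights, and nothing is said about what enters an inflation part. All confidence intervals are to use a robust standard error.

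On the data side, Table 5 in 3.3.3.2 collects "Need for conversion to thoracotomy" as an item describing the intervention. Table 4 in 3.3.3.1 extracts "All ICD-9-CM diagnosis codes present in a SDO", so several complication codes per patient are possible. For the centre questionnaire the reader is referred onward ("details in the data collection form, Annex 2"); that form is not in the text available for this review.

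**The concern.** A zero-inflated model is meant for counts with more zeros than the plain count model can produce. A low event rate does not create that situation: a plain Poisson with mean 0.05 already expects exp(−0.05) = 95.1% zeros.

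Conversion is not a count at all, since an operation is either converted or it is not. Applied to such an outcome, the inflation component has nothing to estimate on the specification that 3.3.4.2 describes. On a richer specification, part of the treatment effect moves out of the coefficient that would normally be reported. At stake is a clean, interpretable estimate for a named robotic-versus-VATS safety comparison.

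**Working it through.** The documents give no conversion risk and no power figure for these outcomes, so there is no stated number to reproduce.

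**Inputs**
- Total for the joint analysis: 5,400 (3.3.4.1).
- Robotic share 0.12 (3.3.4.1): 0.12 × 5,400 = 648.
- VATS share 94/400, from the expected prospective mix (3.3.4.1): 0.235 × 5,400 = 1,269. Applying this share to the whole cohort is an extrapolation.
- Conversion risks in the weighted simulations: 2%/3%, 5%/8% and 8%/15% for the two arms. These are assumptions.
- Confounder in those simulations, also assumed: binary, prevalence 0.5, multiplying risk by 0.4 or 1.6 and shifting the log odds of robotic surgery by ±0.4.

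**Step 1: zeros and variance.** For a yes/no outcome with risk p the zero fraction is 1−p; for a Poisson with the same mean it is exp(−p). Per 1,000 operations:

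| p | yes/no, 1−p | Poisson, exp(−p) |
|---|---|---|
| 3% | 970.0 | 970.4 |
| 8% | 920.0 | 923.1 |
| 15% | 850.0 | 860.7 |

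Since 1−p < exp(−p) for every p > 0, there is a deficit of zeros, never an excess. The variance-to-mean ratio is p(1−p)/p = 1−p, for example 0.85 at p = 15%, so there is no overdispersion either. This step needs no assumed rate; the three risks only illustrate it.

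**Step 2: inflation part with a constant, or with treatment.** Take any fit with inflation probability π > 0 and count mean λ in an arm. Its zero probability is π + (1−π)exp(−λ). The same zero probability is obtained with π = 0 and a smaller λ. Given at least one event, the Poisson probability of exactly one is λ/(exp(λ)−1), which rises as λ falls. In yes/no data every event is exactly one, so the fit without inflation always has the higher likelihood. The argument holds arm by arm and with weights. The maximum is therefore plain (IPW) Poisson, with π on its boundary.

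The simulations agree:
- Unweighted, constant inflation, at four further assumed VATS/robotic risk pairs (2%/1% to 15%/10%), 200 datasets each: largest inflation estimate 0.00002, no gain in log-likelihood over Poisson.
- Weighted, constant or treatment in the inflation part: treatment coefficient within 0.0003 of IPW Poisson on the log scale.
- Weighted zero-inflated negative binomial with dispersion forced positive: dispersion at most 1.6e-8 and coefficient within 0.0001 of IPW Poisson, but 172 of 600 fits did not converge.

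**Step 3: a risk factor in the inflation part.** Step 2 no longer applies, because the zero fraction can now vary with a factor that the count part does not contain.
- Risk factor alone: inflation up to 0.98, standing in for the factor's effect on risk; treatment coefficient within 0.020 of IPW Poisson.
- Treatment and risk factor together: the count-part coefficient moves by a median of 0.10, 0.08 and 0.06 at the three risk pairs. Against the IPW Poisson sampling SDs of 0.359, 0.221 and 0.166 that is 0.10/0.359 = 28%, 0.08/0.221 = 36% and 0.06/0.166 = 36%.
- In the same setting, the effect implied by the whole model, (1−π)λ standardised over the confounder, stayed within 0.0001 of IPW Poisson on the log scale.

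**Step 4: the alternative.** IPW logistic regression converged with a finite robust standard error in 300 of 300 weighted datasets, at full cohort size and risks of 2% or more.

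**The case against.** **The wording is tentative.** The plan only says that the approach will be considered. That is so, and it lowers the weight of the point. Still, no other model is named for these three outcomes, and no rule for choosing one is given.

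**It does little harm as described.** With treatment as the only regressor, zero-inflated Poisson gives the same answer as IPW Poisson with a robust standard error, which is one of the two replacements proposed here. This stands. What remains is a redundant parameter on its boundary and, for the negative binomial version, possible non-convergence. How often that happens depends on the software.

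**A stronger reading is tempting.** With treatment and a risk factor both in the inflation part, the count-part coefficient reversed sign in 9 of 300 simulated datasets. A reader might infer that the conversion result could turn on an unstated modelling choice. The documents do not support that: 3.3.4.2 describes no such inflation part, and the whole-model effect was essentially unchanged. The damage would arise only if the count-part ratio were reported as the total effect.

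**Only conversion is shown to be yes/no.** A reader might extend the criticism to reoperation and complications. The available text does not fix their scale, repeat events or several codes per patient are possible, and Annex 2 could not be checked. Count models may be legitimate there.

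**Logistic regression can struggle with few events.** This also stands. At a 1% robotic risk, 648 × 0.01 is about 6 conversions, and the planned subgroups would have fewer. Zero inflation does not cure sparse data, but the replacement should allow for it.

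**Conclusion.** The point holds in a limited form. Rarity is the only reason given and does not support zero inflation. For conversion there are no excess zeros and no overdispersion to model. That follows by algebra at any risk, given that conversion is recorded once per operation as yes or no, as 3.3.2.2 and Table 5 indicate.

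The practical size is small. On the specification described in the plan, the zero-inflated Poisson estimate is the IPW Poisson estimate, and the negative binomial version may yield no usable fit. On a richer specification, the count-part ratio would mislead if presented as the total treatment effect. The simulated figures rest on assumed risks, one assumed binary confounder and an extrapolated VATS total.

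Minor: only safety outcomes are affected, and long-term survival, the primary efficacy outcome, is not.

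**What to change.** In 3.3.4.2:
- Analyse conversion (VATS versus robotic only), and reoperation and any major complication where coded yes/no, with the IPW logistic model already planned for 30-day death (odds ratio), or with IPW log-link Poisson and the planned robust standard error (risk ratio). Name the effect measure.
- Use a penalised (Firth-type) logistic fit where events are very few, as in subgroups.
- State whether reoperation and complications are analysed as yes/no or as counts per patient. Keep count models for true counts, and add zero inflation only if excess zeros over the plain count model are shown. If it is used, state what enters the inflation part and report the effect implied by the whole model.

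The cost is a few sentences. No new data are needed, sample size and power are unchanged, and the models are simpler to run.

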3.3.4. Data analysis

3.3.4.1. Power of the study

To study the efficacy, data from the retrospective and prospective study will be analyzed jointly. For the retrospective part, approximately 5,000 patients operated on for lung cancer in the participating centers from 01/01/2016 to 12/31/2021 will be included. Based on the average of approximately 450 subjects operated on in the participating centers over 6 months during the years 2019-2021, a sample of 400 subjects eligible for enrollment in 6 months during 2022 was considered in the prospective observational study. As regards the statistical power in the analysis of the primary efficacy outcome, i.e. long-term survival, the calculation was based on an assumption of non-inferiority. The following formula was used to calculate potency in survival studies which is based on the hazard ratio [37].

$$1-\beta=\Phi(z-z_{1-\alpha}), z=(\ln(\theta)-\ln(\theta_0))\sqrt{np_Ap_Bp_E}$$

Where:

- θ_0 = hazard ratio under the null hypothesis, set equal to 1
- θ = observed hazard ratio
- pE = probability of event, i.e. death, set equal to 0.8 on the basis of epidemiological data from the ATS cancer registry
- pA = proportion of treated by robotic surgery equal to 0.12 on the basis of the data present in the SDOs for the year 2019 and of the preliminary information provided by the participating centers

pB = 1-pA

- n = sample size, equal to 5400
- Φ = distribution function of the standard normal
- A = I-type error, set equal to 0
- $1-\beta =$ statistical power

By varying the observed HR of VATS death versus the observed control group between 1.08 and 1.15, the statistical power ranged from 0.5 to 0.91. The power calculation was performed using R (v4.1.2, R Core Team 2021, Vienna, Austria.)

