3.4.4. Sensitivity analysis

Since the costs are volume-dependent, the effect of a different number of cases on the costs and therefore on the cost-effectiveness with respect to the measured volumes will be evaluated. Furthermore, to evaluate the robustness of the model, deterministic sensitivity analyzes will be performed to evaluate the fluctuation of the results as the parameter values vary with respect to the

minimum and maximum of the confidence interval. Univariate analysis will be presented by tornadoplot.

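### The robust standard error for the weighted Cox model is not said to allow for the estimated propensity weights; on its ordinary reading the survival intervals are somewhat too wide if the covariates are prognostic

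*Combined protocol and SAP*

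**What the plan says.** Section 3.3.4.2 (Efficacy study) selects confounders from a causal graph and puts them into a multinomial model for the surgical approach. Candidates are age, gender, performance status, treatment centre and tumour characteristics. The inverse of the estimated probability then weights "regression models (inverse probability weighted, IPW) which will have the outcome as the dependent variable and the treatment modality as the independent variable". So covariates act only through the weights. Long-term survival uses a weighted Cox model. On uncertainty the section says: "All estimates will be presented together with 95% confidence intervals obtained from a robust standard error", with a citation to a paper on the inverse probability weighted Cox model in multi-site studies. It names no bootstrap, stacked estimating equations or doubly robust estimator. The only sensitivity analyses named there change the treatment model.

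Section 3.3.4.3 weights the longitudinal utility model in a similar way. Section 3.4.4 varies each economic input to the "minimum and maximum of the confidence interval".

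Section 3.3.4.1 names long-term survival as the primary efficacy outcome and says that "the calculation was based on an assumption of non-inferiority", but gives no margin. Its power formula contains no term for covariates or for weighting.

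**The concern.** The weights are estimated from the same patients. For weights of the form 1/(estimated probability), with a correctly specified score fitted by maximum likelihood, estimating the score removes chance imbalance in its covariates. If those covariates predict survival, the weighted hazard ratio varies less than it would with known weights. A sandwich variance that treats the weights as known misses this. In large samples it is never smaller than the variance that allows for estimation, and it is larger when the covariates are prognostic.

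The study collects plausible predictors of survival: age, performance status, stage, nodal data and the Charlson index. At stake is precision on the primary efficacy outcome, where the stated power is only 0.5 at the lower end. Excess width in the survival interval would also carry into the tornado plot of 3.4.4 wherever the survival effect is an input.

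**Working it through.** **Inputs from section 3.3.4.1.** "n = sample size, equal to 5400"; "probability of event, i.e. death, set equal to 0.8"; "proportion of treated by robotic surgery equal to 0.12"; "hazard ratio under the null hypothesis, set equal to 1". The type I error is printed as 0, probably cut off in the text.

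**Reproducing the plan's figure.** Information = 5400 × 0.12 × 0.88 × 0.8 = 456.192, so SE(log HR) = 1/√456.192 = 0.0468. Power = Φ(ln HR/SE − 1.645), one-sided 5%:
- HR 1.08: 0.0770/0.0468 gives power 0.50.
- HR 1.15: 0.1398/0.0468 gives power 0.91.
- HR 1.10: 0.0953/0.0468 gives power 0.65.

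The first two match the stated 0.5 to 0.91. A two-sided 5% level gives 0.376 and 0.847 and does not match.

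**Inputs not in the documents (assumed).** Prognostic strength of the score covariates, strength of selection into each approach, and the number and influence of centres. Group shares of 12/23.5/64.5% follow from the expected 48, 94 and 258 patients of 400.

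**Simulation without centre** (n = 5400, about 80% deaths, refitted multinomial score, weighted Cox model, conditional robotic HR 1.15, 400 runs per setting; no, moderate or strong selection). The plain robust SE is compared with a stacked sandwich SE:

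| HR per SD of prognostic score | Stacked/plain width | Plain coverage | Power, plain to stacked |
|---|---|---|---|
| 1.00 | 0.995–0.997 | 94.8–97.5% | no gain beyond 0.2 points |
| 1.35 | about 0.96 | 95.5–97.5% | 86.0 to 87.7; 84.8 to 87.0; 77.2 to 79.0% |
| 1.82 | 0.88–0.89 | 97.5–98.0% | 80.7 to 86.8; 81.2 to 85.5; 68.8 to 76.2% |

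Width ratios of 0.96 and 0.885 mean a plain SE about 4% (1/0.96) and 13% (1/0.885) too large. Stacked intervals covered 93.5–97.0% across the settings with prognostic covariates.

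**Simulation with centre in the score** (8 centres assumed). Plain SE against the true SD of the estimate:
- One set of runs: about 1–11% too large at HR per SD 1.42 and 6–18% at 1.82; about 1–14% with 40% deaths.
- Another set, with assumed centre effects on approach of SD 0.7–1.5 log-odds: on average 3–8% too large at 1.82, 2% at 1.42, and about 0% at 1.42 with 40% deaths and staggered follow-up. At 1.82, single centre configurations ran from −6% to +15%. Each used 200 runs, so an SD carries a relative error of about 1/√400 = 5%.

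So 1–18% is a rough range under assumptions. Values near its bottom arose with centre in the score or with fewer deaths.

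**Power at HR 1.10.**
- Width ratio 0.96 on the plan's SE: 0.0468 × 0.96 = 0.0449, power 0.65 to 0.68.
- A bootstrap that refits the weights gave SE 0.042 against a robust 0.047 (covariates with C-index 0.68). Φ(0.0953/0.047 − 1.645) = 0.65 and Φ(0.0953/0.042 − 1.645) = 0.73, a gain of about 8 points.
- Width ratio 0.885: 0.0468 × 0.885 = 0.0414, power 0.74, the same within simulation error.

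**Other outcomes.**
- 30-day odds ratio, assumed 2% mortality, HR per SD 1.82, 1500 runs: the robust SE was 3–4% smaller than the true SD; coverage 95%.
- Utility difference, n = 400 with 48 robotic patients, simplified to one time point, covariate R² 0.05–0.10: ratio 1.01.
- Stay and operating time were not simulated.

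**The case against.** **The plan does not say that the weights are treated as known.** A robust standard error may or may not include the estimation step, and the cited paper cannot be read here. This stands. The point therefore rests on the ordinary reading of the term. On either reading the sentence needs to say which version is meant.

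**Treatment centre is a named candidate covariate.** If it drives access to the robot but hardly affects death, it adds variance through the weights and earns little prognostic credit. This stands too, and is why the range goes down to about 1%.

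**A reader might infer larger effects.** Stronger covariates do give them: at HR per SD 2.72 the width ratio was 0.77–0.79, with 14–16 points of power lost. The documents give no basis for that strength, and those runs leave out centre. Dividing the plan's 0.0468 by 1.18 would give a power of 0.78 at HR 1.10. But that mixes an unweighted SE with a ratio from a centre-weighted analysis, and compares with a simulation SD rather than an SE that the fix delivered.

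**A reader might also infer** that every weighted interval is too wide, or that survival would be declared inconclusive too often. The runs contradict the first for the 30-day odds ratio and show almost nothing for utility. The second needs a decision rule, and the plan gives neither a margin nor a rule.

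**Conservatism is not invalidity.** Agreed: neither the point estimates nor the validity of the conclusions is in question.

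**Conclusion.** The point holds for the survival hazard ratio. As written, the interval method does not account for estimation of the weights, and its ordinary form is conservative when the score covariates are prognostic. Under assumed moderate prognostic strength the standard error is roughly 1–18% too large. This is worth a few points up to about 8 points of power at HR 1.10, and nothing if the covariates do not predict survival.

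The direction rests on inverse-probability weights from a correctly specified maximum-likelihood score in large samples. The size rests on assumptions that the documents cannot settle. The stated power of 0.5 to 0.91 is not in error on this account, since its formula involves no weighted standard error. For the 30-day odds ratio, stay, operating time and utility no effect is established; with few events or 48 expected robotic patients it may be nil or run the other way. The same limit applies to the tornado plot: only the survival input is shown to be affected.

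**What to change.** In 3.3.4.2, for the survival hazard ratio and, for consistency, the other weighted models (including utility in 3.3.4.3), replace the closing part of the interval sentence, which names the robust standard error, with:

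*… obtained from a patient-level bootstrap, resampled within centre, that refits the multinomial propensity model and recomputes the weights in each resample, or from a sandwich variance that stacks the propensity and outcome equations.*

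Use these limits as the input ranges in 3.4.4.

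The cost is one sentence and computing time, for example 500–1000 refits per model. No new data are needed, and the point estimates and the marginal estimand do not change. Resamples may be unstable for rare outcomes or sparse centre-by-approach cells; the stacked sandwich can be used there. Two limits: the change does not address correlation of outcomes within centres, which the plan leaves open and which could act the other way. And adding covariates to the Cox model instead is not an equivalent remedy, because it changes the estimand: in the simulations a conditional HR of 1.15 corresponded to a marginal HR of 1.10–1.14 when covariates were prognostic.
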